3.4.7.1 Liver Function Tests, Potential Hy's Law and Hy's Law

For the following liver function tests, the multiple of the upper limit of normal (ULN) (reference range) will be calculated for each data point (scheduled and unscheduled): Aspartate aminotransferase (AST), alanine aminotransferase (ALT), total bilirubin, and alkaline phosphatase (ALP):

- Multiple = value/ULN
For example: If the ALT value is 72 IU/L and the ULN 36 IU/L, then the multiple is $72/36 = 2$.

Potential Hy's Law (PHL)

AST or ALT $\geq 3 \times$ ULN **together with** total bilirubin $\geq 2 \times$ ULN at any point during the study following the start of study treatment irrespective of an increase in ALP.

Hy's Law (HL)

A Hy's Law case is defined as any patient with elevations in AST or ALT $\geq 3 \times$ ULN together with total bilirubin level $\geq 2 \times$ ULN, where no other reason, other than the study treatment, can be found to explain the combination of increases, e.g., elevated ALP indicating cholestasis, viral hepatitis, another drug.

For PHL and HL the elevation in transaminases must precede or be coincident with (ie, on the same day) the elevation in total bilirubin level, but there is no specified timeframe within which the elevations in transaminases and total bilirubin level must occur.

Identification of Potential Hy's Law Cases

To identify cases of PHL it is important to perform a comprehensive review of laboratory data for any patient who meets any of the following identification criteria in isolation or in combination:

- ALT $\geq 3 \times$ ULN
- AST $\geq 3 \times$ ULN
- Total bilirubin level $\geq 2 \times$ ULN

3.4.8 ECG

A 12-lead ECG (standard ECG with a paper speed of 25 or 50 mm/second covering at least 6 sequential beats) will be performed as per schedule of assessments (refer to Table 2 of the latest version of the CSP) and will be recorded after the patient has been lying down to rest for at least 5 minutes. After the ECG recording, the investigator or designated physician will review each of the ECGs and record an overall evaluation (normal, abnormal not clinically

significant and abnormal clinically significant). Reasons for abnormal will be collected as part of a free text field.

Patients for whom the ECG assessment was not performed and/or patients with no ECG evaluation, as identified by a “not done” category on the ECG eCRF, will not be presented in subsequent summaries.

3.4.9 Vital Signs

Vital signs (blood pressure and pulse rate) will be measured after 5 minutes rest as per schedule of assessments (refer to Table 2 of the latest version of the CSP). Weight and height assessments will be performed at the visits as shown in Table 2 of the latest version of the CSP.

Change from baseline in vital signs to each post-baseline assessment (scheduled and unscheduled) will be calculated as described in [Section 3.1.3](#).

Vital signs collected at any time during the study (scheduled and unscheduled) will be compared to the pre-defined abnormality assessment criteria reported in [Table 4](#) (refer to Vital Signs Pre-defined Abnormality Assessment Criteria). The assessment of pre-defined abnormalities for systolic blood pressure (SBP), diastolic blood pressure (DBP) and pulse rate will be based on the upper/lower limits as relevant given the patient’s age (years) at the time of the assessment and categorised as:

- Low: Below lower limit of the age-specific abnormality assessment criterion ($< LL$)
- Normal: Within the lower limit and upper limit of the age-specific abnormality assessment criterion, limits inclusive ($\geq LL$ to $\leq UL$)
- High: Greater than upper limit of the age-specific abnormality assessment criterion ($> UL$)

All observed values falling outside these criteria limits will be flagged.

Specifically, change from baseline to maximum/minimum values on-treatment (refer to [Section 3.1.7.1](#)), categorised as described above per abnormality assessment criteria, will be presented, where maximum and minimum vital signs results will be identified as:

- Maximum on-treatment: Highest vital signs result (scheduled or unscheduled value) observed within the period from date of first dose of double-blind randomised study treatment up to and including date of last dose of double-blind randomised study treatment + 7 days.
- Minimum on-treatment: Lowest vital signs result (scheduled or unscheduled value) observed within the period from date of first dose of double-blind randomised study treatment up to and including date of last dose of double-blind randomised study treatment + 7 days.

In addition to the aforementioned assessments, treatment-emergent change from baseline in observed vital signs values (scheduled and unscheduled) will be identified as compared to the relevant abnormality assessment criteria, where treatment-emergent is defined as follows:

- Treatment-emergent = Regarded as treatment-emergent if the post-baseline assessment on-treatment is “worse” than baseline (refer to Section 3.1.7.1 for further details).
 - Increase: In the identification of treatment-emergent high values, change from baseline categories “normal” AND “low” will be considered.
 - Decrease: In the identification of treatment-emergent low values, change from baseline categories “normal” AND “high” will be considered.

For example: Patient 1

SBP	Baseline	Normal	
SBP	Visit 9	Normal	
SBP	Visit 15	High	Treatment-emergent high (increase)

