3.1.2 Baseline

Baseline is the last assessment collected (scheduled or unscheduled) prior to the first dose of study treatment, or last assessment collected prior to or at randomisation (Visit 2), for patients who are randomised but do not receive any study treatment. For in-clinic assessments with an assessment date equal to the first dose of study treatment, the assessment will be assumed to be pre-dose since all assessments are to be done prior to dispensing study treatment according to the protocol. For adverse events (AEs) and concomitant medications with start date equal to the first dose of study treatment, the event will be considered post-baseline.

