3.4.7 Laboratory Variables

Blood samples for safety assessments (clinical chemistry, haematology, urinalysis and coagulation) will be taken as per schedule of assessments (refer to Table 2 of the latest version of the CSP). The list of laboratory variables to be presented in tables, listings and figures are included in Table 4 of the latest version of the CSP. Laboratory tests will be presented using the standardised name.

Laboratory assessments will be summarised and presented for all countries combined, in standard international (SI) units. Laboratory test results obtained from Egypt will be converted to the same SI units per central laboratory specification prior to summary and presentation. Similarly, due to COVID-19, the introduction of local laboratories necessitates the standardisation of local laboratory test results to the same SI units per central laboratory specification, such that data from central- and local laboratories will be combined for summary and presentation in relevant tables.

There will be no imputation for missing values. However, for values recorded with a leading “greater than” or “less than” (>/<) symbol, the reported numeric value will be used for analysis and the value with the qualifier will be included in the patient data listings, unless otherwise specified (e.g., a value of <0.01 will be analysed as 0.01 and listed as <0.01).

Change from baseline in haematology and clinical chemistry assessments (scheduled and unscheduled) will be derived as specified in Section [3.1.3](#).

Laboratory test results (scheduled and unscheduled) will be compared to the relevant laboratory reference range (lower limit of normal [LLN] to upper limit of normal [ULN]), specific to the patient’s age (years) at the time of the assessment and gender as relevant, and categorised as:

- Low: Below lower limit of the laboratory reference range (<LLN)
- Normal: Within the lower limit and upper limit of the laboratory reference range, inclusive (\geq LLN to \leq ULN)
- High: Greater than upper limit of the laboratory reference range (>ULN)

All observed values falling outside these reference ranges will be flagged.

Specifically, change from baseline to maximum/minimum values on-treatment, categorised as described above per laboratory reference range, will be presented, where maximum and minimum laboratory test results will be identified as:

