4.2.9.7 Vital Signs

For the safety analysis set, observed values and change from baseline to each scheduled visit (per planned eCRF visit [number and name]) will be summarised for each vital sign by actual treatment group.

For SBP, DBP and pulse rate, a shift table will be produced presenting the baseline value classification according to abnormality assessment criteria versus the minimum and maximum on-treatment value.

Descriptive statistics, summarising patients with at least one treatment-emergent change (high [increase]/low [decrease]), based on the abnormality assessment criteria, will be presented by actual treatment group. Where:

- n = Number of patients with at least one treatment-emergent change occurring on-treatment (patients with multiple occurrences on-treatment will only be counted once).
- % = Percentage of patients in the safety analysis set with at least one treatment-emergent change occurring on-treatment relative to the total number of patients in the safety analysis set, with a baseline and at least one post-baseline assessment on-treatment available.

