8 APPENDIX

Appendix A Vital Signs Pre-defined Abnormality Assessment Criteria

As far as vital signs are concerned, the following pre-defined abnormality assessment criteria will be considered:

Table 4 Vital Signs Pre-defined Abnormality Assessment Criteria

Years	Systolic Blood Pressure		Diastolic Blood Pressure		Pulse	
	Lower	Upper	Lower	Upper	Lower	Upper
≥ 2 to < 4	80	110	55	75	70	130
≥ 4 to < 6	80	115	55	75	70	120
≥ 6 to < 8	85	115	55	75	65	115
≥ 8 to < 12	90	120	60	80	60	110
≥ 12 to < 14	95	125	65	85	60	110
≥ 14 to < 16	95	130	65	85	55	100
≥ 16 to < 18	95	135	70	85	50	90

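### Treatment-emergent vital-sign flags compare baseline and follow-up on different age limits, so a birthday alone can create a flag

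*SAP*

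**What the plan says.** - **Which readings are classed.** SAP 3.4.9: "Vital signs collected at any time during the study (scheduled and unscheduled) will be compared to the pre-defined abnormality assessment criteria" in Appendix A, Table 4.
- **Which limits apply.** The same section takes the blood-pressure and pulse limits for the patient's "age (years) at the time of the assessment and categorised as" Low, Normal or High.
- **Baseline.** SAP 3.1.2: "Baseline is the last assessment collected (scheduled or unscheduled) prior to the first dose of study treatment". It therefore takes the limits for the child's age on that earlier day.
- **The flag.** SAP 3.4.9: "Regarded as treatment-emergent if the post-baseline assessment on-treatment is" worse than baseline. Worse is then spelled out by class: a high value counts if baseline was Normal or Low, and a low value counts if baseline was Normal or High. No change in the reading itself is required.
- **Where it is reported.** SAP 4.2.9.7 tabulates, by actual treatment group, the number and percentage of patients with at least one such change, labelled as an increase or a decrease. It also gives shift tables of baseline class against the on-treatment minimum and maximum.
- **The limits.** Appendix A introduces Table 4 with "the following pre-defined abnormality assessment criteria will be considered". The table has seven age bands, with steps at 4, 6, 8, 12, 14 and 16 years.
- **Laboratory values.** SAP 3.4.7 uses the same construction, with reference ranges specific to the patient's "age (years) at the time of the assessment and gender as relevant".

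Nothing in SAP 3.4.9, 4.2.9.7 or Appendix A says what to do when a child changes age band between baseline and a later reading.

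**The concern.** Limits for current age are sensible for labelling a single reading. A treatment-emergent flag is a statement about change, and here its two ends are measured on different scales. When a limit tightens at a birthday, a reading lying between the old and the new limit changes class by itself.

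The trial enrols children from 2 to under 18 years and was planned to follow them for 12 to 24 months, with blood pressure and pulse taken at every site visit. Band changes will be common. Vital signs are a named safety outcome, and the false flags all point one way for each sign: low for blood pressure, high for pulse. In a trial of an antiplatelet drug, a reader could take such a pattern as a signal, or a real signal could be harder to see against it.

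**Working it through.** The documents give no figure for this point, so there is none to reproduce.

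**Step 1: unchanged readings that change class.** Limits are from Table 4. Low is below the lower limit, High is above the upper limit, and the limits themselves are Normal.

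| Birthday | Systolic becomes Low | Diastolic becomes Low | Pulse becomes High |
|---|---|---|---|
| 4 | – | – | 121–130 |
| 6 | 80–84 | – | 116–120 |
| 8 | 85–89 | 55–59 | 111–115 |
| 12 | 90–94 | 60–64 | – |
| 14 | – | – | 101–110 |
| 16 | – | 65–69 | 91–100 |

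Every boundary is affected. Two cases at 16 years:
- Pulse 95 at 15 is Normal (55–100). Pulse 95 at 16 is High (50–90). It is flagged as an increase with zero change.
- Diastolic 67 at 15 is Normal (65–85). Diastolic 69 at 16 is Low (70–85). It is flagged as a decrease although it rose.

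**Step 2: the opposite effect.** Upper blood-pressure limits rise and lower pulse limits fall at some boundaries, which hides flags. Systolic 112 at 3 years is High (limit 110), and 118 at 4 years is High (limit 115). There is no flag, because baseline was already High. On the age-4 limits the same child goes from Normal to High.

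**Step 3: how many children cross a boundary.** Assumption, not in the documents: entry age uniform over 2 to 18 years. Bands are at least 2 years wide, so within 24 months a child crosses at most one boundary. The share crossing is 6 × follow-up in years / 16:
- 6 months: 6 × 0.5 / 16 = 19%
- 12 months: 6 × 1 / 16 = 38%
- 18 months: 6 × 1.5 / 16 = 56%
- 24 months: 6 × 2 / 16 = 75%

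**Step 4: how many are flagged with no change in any reading.** Further assumptions: readings start inside the limits, are uniform between them, stay constant, and the three signs are independent. The flagged fraction at each boundary is the strip width over the width of the younger band:
- Diastolic: 5/20 at each of 8, 12 and 16; sum 0.750
- Systolic: 5/35 at 6, 5/30 at 8, 5/30 at 12; sum 0.476
- Pulse: 10/60 at 4, 5/50 at 6, 5/50 at 8, 10/50 at 14, 10/45 at 16; sum 0.789

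For 18 months, multiply by 1.5/16 = 0.09375: low diastolic 7.0%, low systolic 4.5%, high pulse 7.4%.

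For any flag, combine the signs at each boundary as 1 − product of (1 − fraction): 0.167 at 4, 0.229 at 6, 0.438 at 8, 0.375 at 12, 0.200 at 14, 0.417 at 16. The sum is 1.825, and any flag = 1.825 × follow-up / 16.

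**Step 5: vary the spread of readings.** A uniform spread puts many readings near the edges. I also simulated 1,000,000 children with a bell-shaped spread, the limits placed at ±1.96 SD and readings truncated to Normal.

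| Follow-up | Any flag, uniform | Any flag, bell-shaped |
|---|---|---|
| 6 months | 5.7% | 3.0% |
| 12 months | 11.4% | 6.0% |
| 18 months | 17.1% | 9.0% |
| 24 months | 22.8% | 12.0% |

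A bell curve with an SD of one quarter of the limit width, which lets some baselines start outside the limits, gives 2.8% at 6 months and 8.4% at 18 months.

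**Step 6: let readings follow the limits.** With the ±1.96 SD bell shape, the 18-month figure falls from 9.0% to 4.6% if readings move by half the shift in the midpoint of the limits, and to 2.4% if they move by all of it. At 12 months the figures are about 3% and 1.6%.

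**The case against.** The strongest reply has four parts.

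1. **The SAP does what it says.** Worse is defined by class, and moving from Normal for age to Low for age meets that definition. This stands. A reader might infer that the rule contradicts its own condition that the value be worse than baseline; the text does not support that. The problem is that the result is labelled and read as change.
2. **Raw change is reported anyway.** SAP 4.2.9.7 gives observed values and change from baseline by visit, and individual data are listed. This helps, but visit summaries do not show which flagged patients had no change, and the flag table stands alone.
3. **The consequence is small.** SAP 4.2.9 plans no formal analysis of safety data, no efficacy result depends on these flags, and the rule is the same in both arms. This stands. A reader might infer bias between arms; that would need a difference in time on treatment or in age mix, and the documents show neither.
4. **The obvious repair hides real worsening.** Re-judging baseline wholly on the later limits would make a pulse of 95 at 15 already High at 16, so a rise to 140 would go unflagged, as would a diastolic fall from 69 to 50. The current rule flags both. This stands and shapes the fix below.

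**Conclusion.** The defect is real and follows from the written rule. The treatment-emergent vital-sign table will count some children whose reading did not change or moved the other way, always as low blood pressure or high pulse, and it will miss some high-pressure and low-pulse changes.

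The size is uncertain. With constant readings it is roughly 3–6% of patients with at least one false flag in 6 months and 8–17% in 18 months, and less if readings move with age as the limits do. These figures rest on a uniform entry age, independent signs and an assumed spread of readings, none of which the documents give. The 18-month average was a planning figure. SAP 3.1.4.1 records that the sponsor ended the study early, and flags count only on-treatment readings, so the lower part of the range is more likely.

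A reader might take the 17% or 23% figure as the expected rate. It needs a uniform spread, constant readings and 18 or 24 months on treatment together, and the documents do not support that combination. A reader might also carry the size over to the laboratory tables. The construction there is the same, but the reference ranges are not in the documents, so that effect cannot be computed.

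The effect is on reported percentages in a descriptive safety table. It does not touch the primary analysis. The change is worth making because it is cheap.

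**What to change.** Keep limits for age at assessment for the Low, Normal or High label on each reading. In SAP 3.4.9, keep the category rule for treatment-emergent changes and add one condition. Suggested text:

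> A change that meets the category rule is counted as treatment-emergent only if (a) the baseline value lies within the relevant limit for the patient's age at the later assessment, or (b) the later value also lies outside the relevant limit for the patient's age at baseline.

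Check across age 16:

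| Baseline to later reading | Current rule | With the condition |
|---|---|---|
| Pulse 95 to 95 | High flag | None |
| Diastolic 67 to 69 | Low flag | None |
| Pulse 95 to 140 | High flag | High flag, by (b) |
| Diastolic 69 to 50 | Low flag | Low flag, by (b) |
| Pulse 85 to 95 | High flag | High flag, by (a) |

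I checked every pair of whole-number readings from 30 to 179 over all combinations of baseline band and same or later band. With the condition, no flag arises unless the reading moved in the flagged direction.

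Two further changes:
- Footnote the shift tables in SAP 4.2.9.7 to say that limits change with age between baseline and follow-up.
- Apply the same condition in SAP 3.4.7 wherever a laboratory range depends on age.

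Cost: a sentence or two in the SAP, slightly more programming, and no new data. A small move within the strip between old and new limits is no longer flagged when baseline already lay in that strip (for example, pulse 95 to 99 across age 16); the change-from-baseline summaries still include it. The condition only removes flags, so the hidden ones in step 2 stay hidden, and the footnote should say so.

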3.4.10 Physical Examination

For physical examination, only information on whether the assessment was performed or not is recorded. Any abnormal findings are reported as either medical history or adverse events.

3.5 Exploratory Variables

3.5.1 Duration of ACS

Refer to Section 3.3.2 for relevant details.

3.5.2 Pharmacokinetic Parameters

The pharmacokinetic parameters which address the PK properties of ticagrelor and the active metabolite (AR-C124910XX) in oral dose administration are the observed plasma concentrations and the PK parameters, area under the plasma concentration-time curve (AUC) and apparent total clearance of the drug from plasma after oral administration (CL/F) for ticagrelor and AUC for the active metabolite obtained using population PK analysis approach.

PK samples will be collected at 0 hours (pre-dose) and 2 hours post-dose (no pre-dose sample at randomisation [Visit 2]) as per schedule of assessments and in case of changed dose due to weight increase (refer to Table 2 of the latest version of the CSP).

3.5.3 Pharmacodynamic Variables

The pharmacodynamic variable which addresses the PD properties of ticagrelor, as inhibitor of platelet aggregation, is the Platelet Reactivity Index (PRI [%]) measured by vasodilator-stimulated phosphoprotein (VASP) assay.

The PD samples will be collected at 0 hours (pre-dose) and 2 hours post-dose as per schedule of assessments (refer to Table 2 of the latest version of the CSP).

4 ANALYSIS METHODS

4.1 General Principles

4.1.1 General Methodology

The statistical analyses will be performed by IQVIA under the direction of Biometrics, BioPharmaceuticals R&D, AstraZeneca. The data analyses will be conducted using SAS[®] System (SAS Institute Inc., Cary, NC), version 9.2 or higher.

Continuous variables will be summarised for all countries combined, by treatment group by means of descriptive statistics including n (number of patients with available data), arithmetic mean, standard deviation (SD), median, minimum value and maximum value. Quartiles 1 and 3 may be included for some variables where appropriate. The mean and median will be presented with one more decimal place than the original data. Standard deviation with two more decimal places than the original data. Minimum and maximum values with the same number of decimal places as the raw data. In case of a single observation (n=1), SD will be presented as not calculable (set to NC [Not Calculable]) and in case of no observations (n=0) descriptive statistics will be left blank.

For natural log-transformed data, the following descriptive statistics will be presented:

- Number of observations (n)
- Geometric mean (gMean), calculated as $\exp[\mu]$, where μ is the mean of the data on a natural logarithmic scale
- Geometric standard deviation (gSD), calculated as $\exp[s]$, where s is the SD of the data on a natural logarithmic scale
- Geometric coefficient of variance % (gCV%), calculated as $100 \sqrt{[\exp(s^2)-1]}$, where s is the SD of the data on a natural logarithmic scale
- Arithmetic mean (aMean)
- SD
- Median
- Minimum (min)
- Maximum (max)

Categorical variables will be summarised for all countries combined in frequency tables as number (n) of patients and percentage (%) of patients in each category by treatment group. Unless otherwise stated, percentages will be calculated relative to the total number of patients included in the relevant analysis set, by treatment group and overall (if applicable). Percentages will be rounded to one decimal place.

In statistical models, patients will be analysed according to the IxRS stratification level of baseline hydroxyurea use by country (Yes/No) even if this stratum assignment differs to that identified using the CM eCRF. This is in keeping with the intent to treat (ITT) principle.

The significance level for the primary endpoint will be 2-sided 5%; confidence intervals will be 95%. 2-sided p-value < 0.05 will be considered statistically significant.

No multiplicity adjustment will be included as no formal testing on secondary endpoints for statistical significance will be carried out. Statistical testing of secondary efficacy endpoints is only for exploratory purposes.

In general, and unless otherwise specified, ticagrelor data will be pooled and analysed irrespective of weight-based dose (15 mg/30 mg/45 mg bd). Therefore, all summaries will be presented by treatment group as follows:

Ticagrelor 15/30/45 mg bd	Placebo	Total
--------------------------------------	----------------	--------------

Study treatment exposure and compliance, as well as PK and PD data will be analysed according to pooled dose as well as separately per weight-band of dose, overall and/or at the time of assessment, as relevant. Summaries may, therefore, be presented by treatment group as follows, where relevant:

Ticagrelor 15/30/45 mg bd	Ticagrelor 15 mg bd	Ticagrelor 30 mg bd	Ticagrelor 45 mg bd
--------------------------------------	--------------------------------	--------------------------------	--------------------------------

Individual data (scheduled and unscheduled) will be presented in patient data listings. Safety data, PK, and PD listings will be sorted by actual study treatment and E-code number. All other patient data listings will be sorted by patient identifier and planned treatment group.

